4. SELECTION AND WITHDRAWAL OF PATIENTS

4.1. Inclusion Criteria

Patients must meet all the following inclusion criteria to participate in this study:

1. At least 18 years of age or greater at time of informed consent.
2. Diagnosis of either primary open angle glaucoma (POAG) or ocular hypertension (OHT) in each eye.
3. Intraocular Pressure (IOP) Criteria:
 - a. If currently on an IOP-lowering therapy, patient is willing to withhold therapy according to study requirements, and in the opinion of the Investigator, can do so without significant risk.
 - b. If treatment naïve, Screening IOP is ≥ 21 and ≤ 36 mmHg in each eye, and in the opinion of the Investigator, is likely to be controlled on a single IOP-lowering therapy.
 - c. 08:00 Hour IOP is between 21 and 36 mmHg in each eye on Day-1 and Day 1.
4. Central corneal thickness between 480 and 620 μm at Screening in each eye.
5. Best correct visual acuity (BCVA) for distance equivalent to 20/100 or better in each eye at Screening and Day 1 (pre-dose).
6. Able to give signed informed consent and follow study instructions.
7. If patient and/or partner has reproductive potential, agrees to use reliable methods of contraception throughout their participation in the study and until at least 30 days after the last dose.
 - a. If female of childbearing potential, has a negative pregnancy test at Screening and Day-1.

4.2. Exclusion Criteria

A patient who meets any of the following exclusion criteria cannot participate in this study:

Either eye:

1. Mean/Median intraocular pressure > 36 mmHg at Screening and/or any time prior to treatment administration.
2. Concurrent treatment for glaucoma requiring more than 2 topical therapies (either as 2 independent monotherapies or as fixed dose combination), oral IOP-lowering therapy and/or in the opinion of the Investigator cannot be controlled on a single IOP therapy.
3. Has planned ocular surgeries/procedures within the duration of the study.
4. In the opinion of the Investigator has clinically significant dry eye disease that requires chronic use of artificial tears, gels and/or ointments.
5. Any abnormality preventing reliable applanation tonometry.

6. History of closed angle forms of glaucoma and/or Shaffer grade <3 (in 1 or more quadrants); Laser treated narrow anatomic angle is acceptable.
7. Any occurrences of the following prior to Day 1:
 - a. Ocular trauma or surgery within 6 months
 - b. Ocular laser treatments within 3 months
 - c. In the opinion of the Investigator history or evidence of clinically significant ocular inflammation, including but not limited to blepharitis, conjunctivitis, etc.
 - d. History of recurrent ocular herpes (simplex or zoster)
 - e. Previous glaucoma intraocular surgery or glaucoma laser procedure and/or refractive surgery (e.g., radial keratotomy, PRK, SLT, LASIK, etc.) within 6 months
 - f. Ocular medication within 30 days prior, **except for**
 - i. IOP-lowering therapies (washed-out per study requirements)
 - ii. Lid scrubs
 - iii. Artificial tears, gels and/or ointments to treat dry eye disease that in the opinion of the Investigator is not considered chronic use
8. Clinically significant ocular disease (e.g., corneal edema, uveitis, severe keratoconjunctivitis sicca) which might interfere with the study, including
 - a. Glaucomatous damage so severe that wash-out of ocular hypotensive medications for at least 52 days is not judged to be safe (i.e., cup/disc ratio > 0.8)
 - b. Persistent allergic conjunctivitis or allergic conjunctivitis that is likely to manifest during the study and confound the results
 - c. Glaucoma: pseudoexfoliation or pigment dispersion component, congenital, developmental, or secondary (e.g., neovascular, uvetic, pigmentary, lens-induced, steroid-induced, trauma-induced, or glaucoma associated with increased episcleral venous pressure) Note: Previous laser peripheral iridotomy is acceptable.
9. Visual field loss, in the opinion of the Investigator, is functionally significant (e.g., split fixation, mean deviation greater than -20 dB or central fixation point equal to 0 dB, or field defect that is visually significant or likely to cause central visual impairment upon progression) or show evidence of fast (> -1.5 dB/year) progressive visual field loss within the 12 months prior to Day 1.
10. Will require contact lenses and cannot refrain from using them at least 7 days prior to Day 1 and throughout the study.

General/Systemic:

11. Clinically significant lab abnormalities at screening and/or systemic disease which might interfere with the study as per the Investigator's discretion.
12. Participation in any investigational study within 30 days of screening.
13. Changes of systemic medication during the study that could have a substantial effect on IOP (see [5.1.3](#)) within 30 days prior to screening or anticipated during the study.
14. Known hypersensitivity or allergic reaction to cannabinoids, cannabis, sesame seed/oil or any component of the SBI-100 Ophthalmic Emulsion formulation and/or topical anesthetics.

15. Females of childbearing potential (not confirmed as post-menopausal or surgically sterile within the 6 months prior to screening) who are pregnant, nursing, or planning a pregnancy during the study and not using a reliable method of contraception from screening until at least 30 days after the last dose.
16. Males with partners of childbearing potential and do not agree to use a reliable method of contraception during the study and at least 30 days after the last dose.
17. Patients with a history of substance or alcohol abuse, considered chronic tetrahydrocannabinol (THC) users and/or test positive for alcohol or illicit drug use at Screening or Day-1.

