5.2.2. Prevention of Pregnancy

5.2.2.1. Females of Non-Childbearing Potential

All females are considered of childbearing potential unless they are naturally amenorrheic for at least 12 months (post-menopausal) prior to screening and/or are considered surgically sterile. If surgically sterile, medical history within at least 3 months prior to Day 1 of hysterectomy, bilateral salpingectomy, or bilateral oophorectomy.

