5.2.2.2. Females of Childbearing Potential

If of childbearing potential, female patients must not be pregnant, breastfeeding and/or intend to become pregnant during the study. All female patients of childbearing potential must have a negative pregnancy test at Screening and Day-1 and be willing to undergo additional pregnancy test as required throughout the study.

Females of childbearing potential must also agree to use a reliable form of contraception throughout the study until (at least) 30 days after the last dose of study treatment.

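### Exclusion 15 can be read as excluding pregnant, nursing or pregnancy-planning women only if they use no contraception, against 5.2.2.2, and its childbearing-potential window does not match 5.2.2.1

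*Protocol*

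**What the plan says.** Exclusion 15 appears with the same wording in the synopsis and in section 4.2 of the Protocol. It applies to females of childbearing potential "who are pregnant, nursing, or planning a pregnancy during the study and not using a reliable method of contraception". A parenthetical in the same sentence says who counts as being of childbearing potential: those "not confirmed as post-menopausal or surgically sterile within the 6 months prior to screening".

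Section 5.2.2.2 addresses the same women as two separate rules. First, "female patients must not be pregnant, breastfeeding and/or intend to become pregnant during the study". Then, "Females of childbearing potential must also agree to use a reliable form of contraception throughout the study".

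Section 5.2.2.1 treats every female as of childbearing potential unless she is "naturally amenorrheic for at least 12 months (post-menopausal) prior to screening and/or are considered surgically sterile". It adds: "If surgically sterile, medical history within at least 3 months prior to Day 1 of hysterectomy, bilateral salpingectomy, or bilateral oophorectomy".

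Inclusion 7 in section 4.1 requires that a patient with reproductive potential "agrees to use reliable methods of contraception throughout their participation in the study and until at least 30 days after the last dose". Item 7a adds negative pregnancy tests at Screening and Day -1 for females of childbearing potential.

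**The concern.** Exclusion 15 and section 5.2.2.2 govern the same women but differ in logic. The exclusion can be taken to make lack of contraception a further condition for excluding a woman who is pregnant, nursing or planning a pregnancy. Section 5.2.2.2 attaches no such condition. Section 4.3.1 defines a screen failure by the inclusion and exclusion criteria, and the schedule of assessments has sites confirm those criteria before randomization. A rule that stands clearly only in section 5 may therefore not decide who enters.

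What is at stake is exposure the sponsor evidently means to avoid. Section 1.5 states that the human safety profile is not yet established, and treatment runs for 14 days, twice daily, in both eyes. The definition of childbearing potential also decides who is pregnancy-tested and who must use contraception, so two unmatched definitions may be applied differently between sites.

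**Working it through.** No power, sample size or alpha figure bears on this point. The check sets the texts side by side.

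**Step 1. Possible readings of exclusion 15.** Write P = pregnant, N = nursing, L = planning a pregnancy, C = uses reliable contraception. Section 5.2.2.2 permits entry only if not P, not N, not L, and C. It therefore excludes P or N or L or not-C.

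| Reading of *and* in exclusion 15 | Who is excluded | Barred by 5.2.2.2 but not by exclusion 15 |
|---|---|---|
| A. Governs the whole list | (P or N or L) and not-C | P, N or L with C; not-C alone |
| B. Governs planning only | P or N or (L and not-C) | L with C; not-C alone |
| C. Adds a separate group | P or N or L or not-C | none |

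Both readings that take *and* as a true conjunction (A and B) depart from 5.2.2.2. Only reading C agrees with it.

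**Step 2. What the other criteria catch.**
- Pregnancy: inclusion 7a requires negative tests at Screening and Day -1.
- No contraception: inclusion 7 requires agreement to use it.
- Planning a pregnancy during the study: hard to square with that same agreement.
- Nursing: no other inclusion or exclusion criterion mentions it.

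After step 2, the practical gap in the criteria list is N with C under reading A. Under reading B nursing is excluded outright, and what remains is the wording conflict over planned pregnancy.

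**Step 3. Which reading the drafting suggests.** Exclusions 2 and 17 use *and/or* where alternatives are meant. Exclusion 16, the male counterpart, uses a bare *and* as a true conjunction. That gives a site some reason to read exclusion 15 conjunctively, but does not settle the matter.

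**Step 4. Childbearing potential.**

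| Status | Exclusion 15 | Section 5.2.2.1 |
|---|---|---|
| Post-menopausal | confirmed within 6 months before screening | 12 months of amenorrhea before screening |
| Surgically sterile | confirmed within 6 months before screening | "medical history within at least 3 months prior to Day 1 of hysterectomy, bilateral salpingectomy, or bilateral oophorectomy" |

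The stated intervals differ in both rows. For surgery the reference point differs too: screening falls on Day -35 to Day -2, so the two anchors lie about 2 to 35 days apart. The 5.2.2.1 wording on surgery is also unclear in itself, since *within* and *at least* point in opposite directions.

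**The case against.** The best defense is that nobody would apply reading A. It would mean that a pregnant woman is excluded only if she uses no contraception, which is absurd, so a sensible site would take the three states as exclusions in their own right. Section 5.2.2.2 then removes any doubt. Much of this stands: the protocol contradicts itself on nursing but is not silent on it. It does not remove the need for repair, because the criteria list should not depend on the reader rejecting one of its grammatical readings.

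A reader might infer that nothing in the visit schedule could catch a nursing patient. That goes too far. Section 7.1 has sites document medical history, childbearing potential and birth control and assess eligibility. Table 2 repeats the eligibility check at Day -1 and Day 1, and exclusion 15 itself contains the word nursing. What is true is that no visit step separately names it.

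A reader might also infer that the protocol defines menopause by 6 months in one place and by 12 in another. The text does not support this. In exclusion 15 the 6 months attach to when the status was confirmed; the exclusion gives no duration of amenorrhea.

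Nor does a recent hysterectomy show that the two definitions classify a woman differently. Take surgery 4 months before Day 1, at about 30.4 days per month: 4 × 30.4 ≈ 122 days. Relative to screening that is 122 − 35 = 87 to 122 − 2 = 120 days, inside the 6 × 30.4 ≈ 182 days of exclusion 15. If confirmed, she is sterile under both sections.

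Finally, section 9.5 points to 5.2.2 for the definition of childbearing potential. That helps, but exclusion 15 carries its own parenthetical and does not refer there.

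**Conclusion.** The point holds as a drafting contradiction in a safety eligibility rule. Exclusion 15 can be read as excluding some or all of the listed women only if they use no contraception, whereas 5.2.2.2 excludes them outright and requires contraception in addition. Nursing is the one state that no other listed criterion covers.

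On childbearing potential the conclusion is narrower: the interval and reference point in the exclusion 15 parenthetical do not match those in 5.2.2.1. The documents do not show that a particular patient would be classified differently.

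The size is small. Few patients with open-angle glaucoma or ocular hypertension are likely to be nursing; this is a judgment, as the protocol gives no figure. Actual exposure of a nursing patient would need a site both to take the widest conjunctive reading and to overlook 5.2.2.2. No statistical result changes.

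**What to change.** Reconcile exclusion 15 with 5.2.2.2 in both the synopsis and section 4.2. If 5.2.2.2 states the intent, one way is to list four separate exclusions joined by *or*: pregnant; nursing; planning a pregnancy during the study; of childbearing potential without reliable contraception.

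Reconcile the exclusion 15 parenthetical with 5.2.2.1 so that one definition of childbearing potential applies, and have the exclusion refer to it. In doing so, state whether the 6 months is a window for confirming status or a duration, and clear up the wording on surgical history in 5.2.2.1. Which intervals are right is for the sponsor to decide.

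The cost is a sentence in two places and one definition made consistent. No visit, procedure or sample size is affected.

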4.3. Withdrawal Criteria

4.3.1. Screen Failures

Screen failures are defined as patients who consent to participate in the clinical study but do not meet inclusion/exclusion criteria. A minimal set of screen failure information is required to ensure transparent reporting of screen failure patients to meet the Consolidated Standards of Reporting Trials publishing requirements and to respond to queries from regulatory authorities. Minimal information includes screen failure reason, eligibility criteria, and any serious adverse event (SAE).

If a patient is a screen failure due to wash-out from ocular procedures listed in exclusion criteria #7, the Investigator may contact the Medical Monitor and discuss the potential for re-screening in advance of wash-out completion. If the Medical Monitor agrees, the Investigator may schedule a re-screening upon completion of wash-out and file documentation of discussion within their site files.

All other individuals who do not meet the criteria for participation in this study (screen failure) will not be re-screened.

4.3.2. Early Termination of Patients

Patients have the right to withdraw from the study at any time for any reason. An early termination will occur if a patient who signed the informed consent form (ICF) and is dosed ceases participation in the study, regardless of circumstances, before the completion of the protocol defined study procedures.

The Investigator can also withdraw a patient if it is deemed by the Investigator or the Sponsor that it is unsafe for the patient to continue the study. The Sponsor should be notified of early patient discontinuation. Whenever possible, the decision to withdraw a patient should be discussed with the Sponsor.

Patients who require use of rescue medicine should *not be* withdrawn from the trial (5.1.4).

If a patient withdraws consent for disclosure of future information, the Sponsor may retain and continue to use any data collected before such a withdrawal of consent.

If a patient withdraws from the study, he/she may request destruction of any samples taken and not tested, and the Investigator must document this in the site study records.

4.3.3. Procedures for Early Termination

Early patient discontinuation will be clearly documented with date and the reason for discontinuation recorded in the appropriate case report form (CRF).

Reasons for discontinuation:

- Protocol deviation
- Patient non-compliance
- Adverse Event (AE)
- Pregnancy (9.5)
- Investigator decision
- Sponsor decision (if study is canceled)
- Death
- Lost to follow-up
- Withdrawal of consent

If a patient discontinues during the study, all efforts should be made to have the EOS/ET visit procedures completed.

When a patient fails to return for scheduled assessments, efforts should be made to contact them to determine a reason for the failure to return. The site will attempt to contact the patients and reschedule the missed visit within 1-2 days and counsel the patients on the importance of maintaining the assigned visit schedule and ascertain if the patient wishes to and/or should continue in the study. Patients should continue the current dosing regimen until the rescheduled visit.

Before a patient is deemed lost to follow-up, the Investigator or designee will make every effort to regain contact with the patient (3 telephone calls and, if unsuccessful, a certified letter to the patient's last known mailing address or local equivalent methods). These contact attempts must be documented in the patient's medical record or study file.

Should the patient continue to be unreachable, he or she will be considered to have withdrawn from the study with a primary reason of lost to follow-up. Site procedures should follow internal procedures to document attempted contact with the patient. All attempts at contact should be documented in the patient's medical records. If a patient cannot be contacted, they will be considered as lost to follow-up.

All attempts should be made to retrieve the used and un-used study treatment for reconciliation regardless if an EOS/ET visit must be performed with associated documentation.

5. STUDY REQUIREMENTS

5.1. Prior and Concomitant Medications/Procedures

The use of any medications, prescription or over the counter for 30 days prior to screening and for the duration of the study, is to be recorded in the source and subsequently entered into the Electronic Data Capture (EDC) system at each visit.

From screening to the EOS/ET visit, site staff will question each patient specifically on the use of concomitant medications. Site staff must notify the Sponsor immediately if the patient consumes any protocol prohibited medications. Patients who used prohibited medications may be discontinued from the study at the discretion of the Investigator or Sponsor.

5.1.1. Permitted Medications/Procedures

The following medications/procedures are permitted during the study:

- Highly effective contraceptive medication
- Vitamin administration
- Acetaminophen up to 2,000 mg/day (if confirmed as acceptable with Investigator)
- Ocular treatments (noted below) are permitted on Days 2 through 6 and Days 8 through 13. These treatments should **NOT** be used on treatment days or within ± 15 minutes of drop instillation
 - Lid Scrubs
 - Artificial tears, gels and/or ointment to treat dry eye disease

Therapy considered necessary for the patient's welfare may be given at the discretion of the Investigator.

If permissibility of a specific medication/intervention is in question, or if there are any questions regarding concomitant or prior therapy, the Medical Monitor should be contacted.

5.1.2. Prohibited Medications/Procedures

Use of ocular medications other than the study treatment or medications administered to conduct study procedures are prohibited from the screening visit until the EOS/ET visit, to include:

- investigational treatments
- concurrent IOP-lowering therapy
- concurrent or anticipated use of topical ocular medication and/or steroids.
- Planned invasive ocular procedures and/or surgeries.
- Changes in beta blocker, diuretics and/or any other medication changes that impact IOP as per Investigator discretion.

5.1.1 notes medications that are permitted. The decision to administer a prohibited medication/treatment will be made with the safety of the study patient as the primary

consideration. When possible, the Sponsor should be notified before the prohibited medication/procedure is administered.

5.1.3. Wash-out of IOP-Lowering Therapies

Treatment naïve patients that meet eligibility criteria may be scheduled for Day-1.

If the patient is currently being treated with an IOP-lowering therapy, it is to be withheld prior to Day-1 based on type of treatment in accordance with the following schedule:

~28 days (additional days can be added as per Investigator discretion)	β-adrenoceptor antagonists, prostaglandins, rho-kinase inhibitors
14 days	adrenergic agonist, sympathomimetics
5 days	Muscarinic agonist, carbonic anhydrase inhibitors (CAI)

5.1.4. Rescue Medication/Therapy

Any patient who has an elevated IOP that the Investigator considers unsafe may be rescued and placed on an alternative therapy. The choice of therapy is the Investigator's discretion.

The following guidance may assist Investigators for rescue therapy, however, the decision to rescue is at the discretion of the Investigator's judgement:

- Outside of study treatment, ocular hypotensive medications are prohibited for the duration of the study unless rescue therapy is required for a specific patient.
- If the patient's IOP is > 36 mmHg, the Investigator may re-check the IOP within 1 day of the visit and rescue therapy may be considered if the IOP remains elevated.
- The reason a patient requires rescue medication/therapy (i.e., elevated IOP) can be considered an AE and should be documented as a treatment failure. However, the act of a patient requiring rescue is not considered an AE.
- The choice of rescue medication prescribed will be entered in the concomitant medications page of the CRF, noting that it was used as a rescue therapy.
- Patients who require the use of rescue medication should discontinue use of the study treatment but will continue to be followed for safety purposes and should not be withdrawn from the study.

5.2. Study Restrictions

5.2.1. Contact Lens Use

The use of contact lenses is not permitted during the study. Patients who wear contact lenses must cease use of contact lenses at least 7 days prior to Day 1 and for the duration of the trial.

5.2.2. Prevention of Pregnancy

5.2.2.1. Females of Non-Childbearing Potential

All females are considered of childbearing potential unless they are naturally amenorrheic for at least 12 months (post-menopausal) prior to screening and/or are considered surgically sterile. If surgically sterile, medical history within at least 3 months prior to Day 1 of hysterectomy, bilateral salpingectomy, or bilateral oophorectomy.

